11.9 Source Documentation.....	37
11.10 Subject Confidentiality/Record.....	37
11.11 Data Management.....	37
12.0 Regulatory / Ethical Considerations.....	37
12.1 Role of JJMS.....	37
12.2 Maintaining Records.....	37
13.0 References.....	38

The Effectiveness and Safety in the treatment of CPVI for Symptomatic Paroxysmal Atrial Fibrillation with THERMOCOOL® SMARTTOUCH™ Catheter in China——A Multi-center Clinical Registry Study (SMART CHINA)

Protocol Summary

Title:	The Effectiveness and Safety in the treatment of CPVI for Symptomatic Paroxysmal Atrial Fibrillation with THERMOCOOL® SMARTTOUCH™ Catheter in China——A Multi-center Clinical Registry Study (SMART CHINA)
Design:	This is a prospective, multicenter, non-randomized clinical evaluation utilizing the THERMOCOOL® SMARTTOUCH™ catheter undergoing CPVI compared to a pre-determined performance goal.
Purpose:	The purpose of this study is to assess the effectiveness and safety of the THERMOCOOL® SMARTTOUCH™ catheter in the treatment of drug refractory symptomatic paroxysmal atrial fibrillation (PAF) undergoing CPVI.
Enrollment:	Approximately 200 patients will be enrolled (minimum 188).
Clinical Sites:	Up to 15 sites in China.
Study Duration:	9 months enrollment period (adjust the progress according to the actual status) and follow-up at 3, 6, 9 and 12 months after CPVI. Blanking period will span 90 days after CPVI.
Study Population:	Subjects with drug refractory symptomatic PAF who have had at least one (1) AF episode in the 12 months prior to enrollment and have failed at least one antiarrhythmic drug (AAD).
Primary Endpoint:	The primary effectiveness endpoint for this study is freedom from documented symptomatic atrial fibrillation (AF), atrial tachycardia (AT), or atrial flutter (AFL) episodes through 12-month follow-up after the index CPVI procedure.
Secondary Endpoints:	Acute success rate at 0.5h post CPVI (entrance block after CPVI are achieved in all veins with an isoproterenol intravenous challenge) CF and Force Time Integral (FTI) for index procedure by PV segments (from PV to the atrium, divided into 3, 6, 9 and 12 point positions)

Number, percentage and sites of Pulmonary vein(PV) reconnection after index procedure(from PV to the atrium, divided into 3, 6, 9 and 12 point positions)

Total procedural, ablation time and fluoroscopy time

The incidence of AEs related with the procedure and study catheter

List of Acronyms/Abbreviations and Study Terms/Definitions

Acronym/Abbreviation	Expanded Term
AAD	Antiarrhythmic Drug
ACC/AHA/ESC	American College of Cardiology/American Heart Association/European Society of Cardiology
AE	Adverse Event
AF	Atrial Fibrillation
AT	Atrial Tachycardia
CABG	Coronary artery bypass graft surgery
CRF	Case Report Form
CVA	Cerebrovascular Accident or Stroke
EC	Ethics Committee
ECG	Electrocardiogram
EP	Electrophysiology
GCP	Good Clinical Practices
HM	Holter Monitoring
HRS/EHRA/ECAS	Heart Rhythm Society/European Heart Rhythm Association/European Cardiac Arrhythmia Society
ICD	Implantable Cardioverter Defibrillator
ICF	Informed Consent Form
IFU	Instructions For Use
LA	Left Atrium
LV	Left Ventricle
MI	Myocardial Infarction
PAF	Paroxysmal Atrial Fibrillation
PI	Principal Investigator
PV	Pulmonary Vein
PVI	Pulmonary Vein Isolation
RA	Right Atrium
RF	Radiofrequency
RV	Right Ventricle
SAE	Serious Adverse Event
TEE	Transesophageal Echocardiography
TIA	Transient Ischemic Attack
TTE	Transthoracic Echocardiography
UADE	Unanticipated Adverse Device Effect

1.0 Introduction

1.1 Background

Redacted

1.2 Rationale

Redacted

1.3 Device Description

The commercially available THERMOCOOL™ SMARTTOUCH™ catheter Diagnostic /Ablation Deflectable Tip Catheter with Contact Force Sensing Capability is the only study catheter to be used in this study.

The catheter is a multi-electrode luminal catheter with a deflectable 3.5 mm tip designed to facilitate electrophysiological mapping of the heart and to transmit RF current to the catheter tip electrode for ablation purposes. The catheter shaft measures 7.5 F with 8.0 F ring electrodes. For ablation, the catheter is used in conjunction with an RF generator and a dispersive pad (indifferent electrode).

The catheter has force sensing technology that provides a real-time measurement of contact force between the catheter tip and the beating heart wall. It is specifically designed to allow full integration with the electro-anatomic mapping system, which provides both graphical and numerical displays of CF and the force vector in real time; thus both magnitude and direction of the force are visualized via a 3-D vector. This catheter is a modification of the widely used irrigated-tip bidirectional diagnostic/ablation catheter (THERMOCOOL® EZ Steer™, Biosense Webster) and diagnostic/ablation I catheter (NAVISTAR THERMOCOOL™, Biosense Webster), using a similar irrigation and bidirectional system. Only the distal tip has been modified with additional elements to accomplish CF sensing.

The VisiTag™ Module software is a novel algorithm that has been developed, which automatically tags the RF catheter ablation applications on the Carto® 3 Mapping System. Adhesive electrical dispersive pads for the RF current return path and available equipment for recording multiple intra-cardiac electrograms and signals from the RF generator (i.e., power, temperature, impedance) in electrical stimulation will be used.

Study participants who undergo PVI are to have their procedure performed and completed (as described in section 5.4) using the study device in conjunction with the CARTO® 3 System (version 3.2 or higher), an electro-anatomic mapping system for use in performing catheter-based electrophysiological RF ablation procedures. All devices to be used in this study are commercially available, conform to the applicable local regulations and are to be used according to the approved indication and their Instructions for Use (IFU). Each site will be required to have specific equipment for performing RF ablation procedures. Sites will be instructed to refer to the User's Manual / Instructions for Use for the set-up of system / device / component.

1.4 Risk analysis

RF catheter ablation has been used for nearly two decades. The use of saline-irrigated ablation catheter is routine for many PAF ablation procedures whose risks and complications are well understood.

1.4.1 Description and Analysis of Risks

The incremental risk associated with performing RF catheter ablation using the THERMOCOOL® SMARTTOUCH™ catheter, which includes contact force sensing technology, is small relative to that of a standard electrode catheter that does not include this technology. The larger RF lesion size produced with this catheter may increase pain (during the procedure) associated with RF applications and may increase the risk of cardiac rupture. Increased pain, however, can be managed with intravenous analgesics. Additionally, use of the cooled electrode tip catheter may reduce procedural time, fluoroscopy time and increase procedural success by increasing lesion depth and by minimizing thrombus formation, which necessitates repeated removal and re-deployment of the ablation catheter. While the ability to cool the electrode-tissue interface allows the use of higher power than with a conventional 4mm electrode, RF power in the range of 30-40 watts is often adequate. For any given power setting, the power delivered to the tissue is similar to that used with a 4mm electrode.

Radiofrequency current may cause occlusion of a coronary artery, either by direct thermal damage, spasm, or thrombosis. Experience at numerous centers suggests that the risk of coronary occlusion is less than 0.5%.^{35,36} Coronary artery occlusion could produce myocardial infarction (MI), angina or death. Should occlusion of a coronary artery occur for any reason, the investigator will attempt to restore coronary blood flow through pharmacological, catheter and/or surgical intervention, as medically indicated.

The application of radiofrequency current close to the AV node or His bundle could damage or destroy the normal AV conduction system, producing complete heart block and requiring implantation of a permanent pacemaker.

A thrombus may form on the ablation electrode during the application of radiofrequency current without any change in impedance. The thrombus might become dislodged and embolize to produce a stroke, MI, or other ischemic injury. The risk of an embolus is reduced by quickly terminating the application of current after an impedance rise, which limits the size of the thrombus on the electrode. Probably the most important aspect of the THERMOCOOL® family of catheters is the near absence or very low likelihood of thrombus formation during RF.

Thrombus formation on the endocardium following ablation may produce an arterial or pulmonary embolus. This risk may be reduced by the use of aspirin (antithrombotic) and/or anticoagulation therapy, at the discretion of the investigator.

Cardiac perforation may result from catheter manipulation or application of radiofrequency current (risk is <1%).^{35,36} This may result in cardiac tamponade and may require percutaneous pericardial drainage or surgical repair. Significant hemodynamic compromise can result in neurologic injury or death. An increased risk of cardiac perforation may be associated with the use of a saline-irrigated electrode catheter due to its ability to create a larger, deeper RF lesion. This risk is greatest in a thin walled chamber (i.e., RA, LA, or RV); however, the risk of perforation related to a deep steam pop is reduced if RF energy is not delivered perpendicular to the wall at power above 35 or 40 watts. If the lesion is deeper, the risk of steam pop is higher above 35-40 watts.

Injury to a cardiac valve may result from catheter manipulation or the application of radiofrequency current (risk <1%).³⁵⁻³⁷ This may produce valvular insufficiency and possibly necessitate valve replacement surgery.

The application of RF current along the posterior left atrium can result in thermal injury to the esophagus and the formation of an atrio-esophageal fistula. This is a very rare (0.04%) but severe complication of RF ablation that may require surgical intervention or result in permanent impairment.³⁷ Reducing power at sites in close proximity to and/or avoiding sites directly over the esophagus may reduce the risk of thermal injury.

Injury to the phrenic nerve may occur as a result of RF application in the region of the right pulmonary veins. The reported incidence of phrenic nerve injury varies from 0% to 0.48% when RF energy is used for catheter ablation.³⁷ Prior to ablation in the region of the RSPV, investigators are encouraged to perform precautionary measures, such as evaluation of proximity to the phrenic nerve and pacing maneuvers.

Radiation exposure during fluoroscopic imaging of catheters may result in an increase in the lifetime risk of developing a fatal malignancy (0.1%) or a genetic defect in offspring (0.002%).³⁸⁻⁴⁰

The risk of pulmonary AEs (e.g., pulmonary vein stenosis, thrombus and hypertension), associated with an AF ablation procedure targeting the pulmonary veins, is considered small (<4%).^{23,41-47}

Other potential complications, which may result from catheter insertion and manipulation as part of the prerequisite electrophysiology study and mapping procedure, include: Allergic reaction to the local anesthetic, sedatives, x-ray dye, heparin, protamine, or other agents administered during the procedure (risk <1%).⁴⁸⁻⁵² Arterial or venous injury, including arterial dissection, thrombosis, occlusion or hemorrhage at the catheter insertion sites or at other

sites along the vessels (risk <1%),^{35,36} which may produce hemorrhage, hematoma or ischemic injury to an extremity or major organ. Hemorrhage as a result of anticoagulation (risk <0.5%), which may require transfusion.^{35,36} Infection, either at the catheter insertion site or systemically, including endocarditis and septic emboli (risk <0.5%);³⁵⁻³⁷ this risk can be minimized by using standard aseptic technique and by the use of antibiotic agents when indicated.

1.4.2 Minimization of Risks

The criteria for subject selection, methods, personnel, facilities, and training that have been specified for this study are intended to minimize the risk to subjects undergoing this procedure. Subjects will be screened carefully prior to enrollment in the study to confirm compliance with the study inclusion and exclusion criteria.

Participating investigators will be experienced and skilled in performing electrophysiology studies, intracardiac mapping, and ablation of AF with the use of the RF ablation catheters. Operators will have >50 AF ablation case per year experience, and before study initiation, they will perform CF-guided ablation in 5 patients to become familiar with CF monitoring and decrease learning curve-associated bias. Procedures will be performed in electrophysiology laboratories, with the assistance of skilled nurses and technicians. The laboratory will contain sufficient resuscitative equipment and facilities to manage any potential complication. Cardiac surgical facilities, as well as a qualified cardiovascular surgeon, will be available during the ablation procedure in the event that surgical intervention becomes necessary.

Ablation procedures with the THERMOCOOL® SMATTOUCH™ catheter will be performed according to the product Instructions for Use, including but not limited to instructions regarding indications and contraindications for using these devices.

1.4.3 Precautions

Invasive electrophysiological evaluation and catheter ablation may impart some degree of risk to the patient. The risk of serious complications is generally related to the severity of cardiac disease. The degree of risk of the electrophysiological and catheter ablation procedures and the potential benefit of the treatment of symptomatic PAF should be determined by a qualified physician. Failure to observe all contraindications, warnings, and precautions, as listed in the Instructions for Use may result in procedural complications. Procedural complications include: cardiovascular injury or perforation with or without cardiac tamponade, pericardial effusion, esophageal fistula, severe PV stenosis, pulmonary embolus, tricuspid regurgitation, MI, bleeding at the catheter insertion site, sepsis, stroke, and death.

1.4.4 Potential Benefit

The direct benefit for patients undergoing radiofrequency catheter ablation is the potential elimination of AF episodes. It is furthermore expected that quality of life will improve and less frequent hospitalization will be required. The information gathered during the conduct of this study may be of benefit in the future for the treatment of patients with atrial fibrillation.

2.0 Study Objective

The purpose of this study is to assess the effectiveness and safety in the treatment for drug refractory symptomatic paroxysmal atrial fibrillation (PAF) subjects with the THERMOCOOL® SMARTTOUCH™ catheter undergoing CPVI.

3.0 Basic Study Design

This is a prospective, multicenter, non-randomized clinical evaluation utilizing the THERMOCOOL® SMARTTOUCH™ catheter undergoing CPVI compared to a pre-determined performance goal. Approximately 200 subjects (minimum 188) will be enrolled at up to 15 sites in the China.

3.1 Screening

All patients considered for a RF ablation procedure for drug refractory recurrent symptomatic PAF should be screened by the investigator or designated member of the research team for study eligibility.

Symptomatic Episode: symptom(s) which is/are concurrent with a documented episode of AF by either ECG, Holter monitor (HM), or TTM. Symptoms may include but are not limited to: palpitations, irregular pulse (eg, tachycardia or bradycardia), dizziness, weakness, chest discomfort, and breathlessness.

3.2 Informed Consent Form (ICF)

Informed consent is mandatory and the informed consent form signed and dated by both investigator and subject must be obtained from all subjects prior to CRF entering in this study. Any modifications to the Patient Informed Consent Form must be approved by JJMS and the IEC. The copy of Informed Consent Form approved by IEC along with the copies of consent forms signed by every subject must be maintained by every investigator in a designated clinical trial master file. A signed copy of the consent form must be given to each subject. It is the investigator's responsibility to ensure that the Informed Consent process is performed in accordance with GCP.

3.3 Number of Centers

Up to 15 sites in China will participate in this study. Total enrollment among all sites of up to 200 subjects is expected. Sites participating in this study will be selected based upon their capabilities to successfully carry out those assessments.

CPVI will be performed by experienced operators who have prior experience with the NAVISTAR® THERMOCOOL® and/or EZ STEER® THERMOCOOL® NAV catheters (>50 AF ablation case per year). Before study initiation, operators will be trained on the use of the CF-guided ablation catheter and CARTO®3 VisiTag module for at least 5 patients. Investigators will set

personal operating reference ranges using experience gained from this training and the information of the prior clinical (human) studies and published literature. These patients will not be included in the study.

3.4 Subject Selection - Inclusion Criteria

Candidates for this study must meet ALL of the following criteria:

1. Age 18 years or older
2. Failure of at least one antiarrhythmic drug (AAD) for AF (class I or III, or AV nodal blocking agents such as beta blockers and calcium channel blockers) as evidenced by recurrent symptomatic AF, or intolerance to the AAD
3. Patients with paroxysmal AF eligible for catheter ablation
4. Patients with symptomatic PAF who have had at least one documented AF episode in the twelve (12) months prior to enrollment. Documentation may include but is not limited to electrocardiogram (ECG), Holter monitor (HM) or transtelephonic monitor (TTM)
5. Able and willing to comply with all pre-, post- and follow-up testing and requirements
6. Be able to sign IRB/EC-approved informed consent form

3.5 Subject Selection - Exclusion Criteria

Candidates for this study will be EXCLUDED from the study if ANY of the following conditions apply:

1. AF secondary to electrolyte imbalance, thyroid disease, or reversible or non-cardiac cause
2. Previous surgical or catheter ablation for AF
3. Any PCI, cardiac surgery, or valvular cardiac surgical or percutaneous procedure (e.g., ventriculotomy, atriotomy, and valve repair or replacement and presence of a prosthetic valve) within the past 2 months.
4. Any carotid stenting or endarterectomy.
5. Coronary artery bypass graft (CABG) procedure within the last 180 days (6 months)
6. AF episodes lasting longer than 7 days or terminated via cardioversion
7. Documented left atrial thrombus on imaging
8. Uncontrolled heart Failure or New York Heart Association (NYHA) class III or IV
9. Myocardial Infarction within the previous 60 days (2 months)
10. Documented thromboembolic event (including TIA) within the past 12 months
11. Rheumatic heart disease
12. Awaiting cardiac transplantation or other cardiac surgery within the next 365 days (12 months)
13. Significant pulmonary disease, (e.g., restrictive pulmonary disease, constrictive or chronic obstructive pulmonary disease) or any other disease or malfunction of the lungs or respiratory system that produces chronic symptoms.
14. Significant congenital anomaly or medical problem that in the opinion of the investigator would preclude enrollment in this study
15. Active illness or active systemic infection or sepsis
16. Diagnosed atrial myxoma

17. Unstable angina within the past 60 days (2 months)
18. History of blood clotting or bleeding abnormalities
19. Life expectancy less than 365 days (12 months)
20. Hypertrophic obstructive cardiomyopathy
21. Presence of implanted ICD
22. Contraindication to anticoagulation
23. Contraindication to isoproterenol
24. Presence of intramural thrombus, tumor or other abnormality that precludes catheter introduction or manipulation
25. Presence of a condition that precludes vascular access.
26. Women who are pregnant and/or breast feeding
27. Patients presenting contraindications for study catheter(s), as indicated in the respective Instructions For Use
28. Enrollment in an investigational study evaluating another device, biologic, or drug.

3.6 Subject Disposition

- **Enrolled Subjects:** patients who sign the informed consent.
- **Excluded Subjects:** subjects that are enrolled but never undergo insertion of the Study Catheter. Excluded subjects will not be evaluated in this study.
- **Discontinued Subjects:** subjects that have the investigational catheter inserted but are not treated with the investigational device (ie, no RF energy applied). Subjects will be categorized as "discontinued" if ablation was not possible due to non-investigational equipment failure or if their arrhythmia was determined at the time of electrophysiologic study to be a non-study arrhythmia (eg, atrial flutter).
- **Lost to Follow-up Subjects:** all subjects should be encouraged to return for protocol required office, clinic visit for evaluation during the study follow-up period. If a subject is unable to return for an office or clinic visit or unable to be contacted by telephone, 3 separate telephone calls should be made to obtain subject related safety information. All attempts should be documented in the source documents. If the subject does not respond to the 3 telephone calls, then the investigator must send a certified letter to the subject. If the subject does not respond to the letter, then the subject will be considered "lost to follow-up" for the current study visit. Subject contact must be attempted at each follow-up time point and if unable to contact the subject after 3 phone calls, the subject should once again be sent a certified letter. Only after failing to contact the subject at the final follow-up visit, the subject will be considered lost to follow-up and the study termination will be recorded in the individual case report form.
- **Withdrawn / Early Termination Subjects:** The investigator may remove a subject from the study for any of the following reasons: no longer meets eligibility criteria; withdrawal is in the subject's best interest; subject preference; concurrent illness; noncompliance; or any other situation the investigator deems a compromise to the integrity of the study. Subjects will be informed prior to study entry that they are free to withdraw from the study at any time and for any reason, without prejudice to his or her future medical care by the physician or the institution.

If a subject is removed from the study, the date and reason for withdrawal will be recorded on the appropriate case report form (CRF). If the subject is withdrawn due to an adverse event (AE) or serious adverse event (SAE), the Investigator must comply with all reporting requirements and must follow the subject until the AE/SAE has resolved or stabilized.

- **Completed Subjects:** enrolled subjects who have not expired or been discontinued, withdrawn or lost-to-follow-up from the study, prior to the final 1-year study visit.

4.0 Study Endpoints

4.1 Primary Effectiveness Endpoint

The primary effectiveness endpoint for this study is freedom from documented symptomatic atrial fibrillation (AF), atrial tachycardia (AT), or atrial flutter (AFL) episodes through 12-month follow-up after the index ablation procedure (includes a three-month blanking period).

AF/AFL/AT qualifies as an arrhythmia recurrence after the first ablation if it lasts ≥ 30 seconds and is documented by ECG, HM or TTM, etc.

The following will also be considered primary effectiveness failures and will be included in the effectiveness analysis cohorts:

- Acute procedural failure (ie, failure to confirm entrance block in all pulmonary veins with an isoproterenol intravenous challenge 0.5h post procedure or use of a non-study catheter to treat the study arrhythmia)
- A repeat ablation beyond the 90-day blanking period

Atrial tachyarrhythmia recurrence events will be recorded and included in study analysis after a 90-day blanking period; recurrence during the blanking will not be considered treatment failure; re-ablation will not be recommended during the blanking^{12,53}.

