5.7 Management of Arrhythmia Recurrence During Follow-up

Repeat AF ablations(s) may be performed at the discretion of the physician in accordance with current AF management guidelines.^{11,13,32-34,53} The follow-up schedule will remain based on the initial AF ablation procedure performed with the Study Catheter. All re-ablation procedures must be fully documented in CRF.

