8.2 Sample Size and Power Calculation

Assuming the true rate for freedom from documented symptomatic AF, AT, or AFL episodes through 12-months follow-up is about 65% with CF-guided approach and a historic control performance goal of 50%,¹² a sample size of 150 is needed in order to have 95% power to have the lower bound of the two-sided 95% confidence interval of this recurrence free rate above the historic control performance goal. This sample size is computed using nQuery Advisor® version 7.0. Considering 20% dropout rate, a sample size of 188 is needed. This study will enroll approximately 200 subjects (no less than 188).

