6.2.3 Per-protocol (PP) Population

Per-protocol (PP) Population: Subjects in the ITT Population who have undergone insertion of the study catheter and AF ablation procedure, and do not have other major protocol violations. The definition of major protocol violations includes but not limited to:

- Serious violation of the inclusion/exclusion criteria, and the subjects are allowed to continue the clinical trial;
- Violation of informed consent (e.g.: no informed consent is conducted, the signature and/or the date of the informed consent form is missing; The time signed is after the procedure; Both the two copies of ICF are kept in the study site)
- No transesophageal echocardiography (TEE) examination is conducted within 24 hours before the procedure; (Applicable to the document “A Description of SMART CHINA Study Protocol Violations/Deviation Report to Institutional Ethics Committee(IEC)” developed on June 20, 2015)
- No examination to detect LA thrombi is conducted before the procedure; (Applicable to the document “A Description of SMART CHINA Study Protocol Violations/Deviation Report to Institutional Ethics Committee(IEC)” developed on January 18, 2016)
- THERMOCOOL® SMARTTOUCH™ catheter is not used or is used repeatedly during the procedure
- CARTO®3 V3.2 or the later version and VisiTag™ software is used for data collection during the procedure
- No isoproterenol is used to confirm entrance block 30 minutes after the procedure
- Agilis sheathing canal in combination with THERMOCOOL® SMARTTOUCH™ catheter is used during the procedure

Repeated ablation treatment is conducted during the blanking period, PP population will be used to provide supportive analysis for efficacy endpoints.

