6.5 Effectiveness Analysis

6.5.1 Primary Efficacy Endpoint Analysis

ITT population is used for the main analysis of the primary endpoint, and PP population is used for supportive analysis.

The primary endpoint for this study is freedom from documented symptomatic AF, AT, or AFL episodes through 12-months follow-up after the index ablation procedure (includes a 3 months blanking period).

The following will also be considered primary effectiveness failures and will be included in the effectiveness analysis population:

- Acute procedural failure (i.e., failure to confirm entrance block in all pulmonary veins with an isoproterenol intravenous challenge 0.5 h post procedure or use of a non-study catheter to treat the study arrhythmia);
- A repeated ablation after the 90-day blanking period

Atrial tachyarrhythmia recurrence events will be recorded and included in study analysis after a 90-day blanking period. Recurrence during the blanking will not be considered treatment failure.

The number of subjects who achieved this endpoint and its percentage will be presented. A two-sided binomial exact 95% confidence interval will be computed. Superiority against historic control performance goal (50%) after applying THERMOCOOL® SMARTTOUCH™ catheter with contact sensitivity will be claimed if the lower bound of this confidence interval is above 50%.

For the subjects failing to be followed up to the primary endpoint, with conservative consideration, these subjects are considered as primary effectiveness endpoint failure in the main analysis.

Sensitivity analysis will be conducted for the primary endpoints using the methods below:

- For the subjects failed to be followed up to the primary endpoint, the primary endpoint is considered as missing in the analysis, and the subjects will be excluded from ITT analysis set.

A Kaplan-Meier analysis will be performed for the time to the first documented symptomatic AF, AT, or AFL episode. The first quartile, median, third quartile and 95% confidence intervals of the first quartile, median and the third quartile will be computed.

Kaplan-Meier curves for episode time of symptomatic AF, AT or AFL first recorded during 12 months follow-up (Day 91 to 361) after the first ablation will be presented.

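### A repeat ablation inside the 90-day blanking period is not itself a failure in any planned analysis, so the single-procedure success rate is never estimated

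*Protocol*

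**What the plan says.** - **Endpoint.** Protocol 4.1 and SAP 4.1 and 6.5.1 define success as no documented symptomatic AF, AT or AFL through 12 months, counted from the index ablation and with a three-month blanking period.
- **Repeat ablation as failure.** Protocol 4.1 lists "A repeat ablation beyond the 90-day blanking period". SAP 6.5.1 lists "A repeated ablation after the 90-day blanking period". Neither lists a repeat ablation within the 90 days. Protocol 4.1 also states that arrhythmia recurrence in blanking is not a failure.
- **Status of early re-ablation.** Protocol 4.1 does not recommend it. Protocol 5.7 leaves repeat ablation to the physician's discretion with no restriction for blanking, and adds: "The follow-up schedule will remain based on the initial AF ablation procedure performed with the Study Catheter". Protocol 5.5 and SAP 3.7 likewise do not reset the visit schedule.
- **Per-protocol set.** After the list of major violations, SAP 6.2.3 has a sentence that begins "Repeated ablation treatment is conducted during the blanking period" and then runs into the statement of what the PP set is for. It looks like a last list item that lost its line break.
- **Other analyses.** The one sensitivity analysis in SAP 6.5.1 changes only how incomplete follow-up is handled. The Kaplan-Meier curve there covers Day 91 to 361. The re-ablation summary in the same section covers only procedures after blanking.

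**The concern.** Blanking exists so that early, possibly transient arrhythmia is not scored against the procedure. A second ablation is a different matter: once it has been done, later freedom from arrhythmia can no longer be credited to the index procedure alone. Under the listed rules, a subject re-ablated on Day 60 and event-free afterwards is an ITT success of the index procedure. If PP excludes that subject, the supportive analysis selects on something that happened after treatment and suggests that the index procedure did not hold.

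The ITT figure can therefore mix one- and two-procedure success, and the PP figure may leave out some early index failures. Both would lie at or above the single-procedure rate. The trial is a single-arm comparison with a fixed 50% goal, so no control group would share and cancel the difference.

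**Working it through.** **1. The plan's own figures.** Protocol 8.2 assumes that success through 12 months of "follow-up is about 65% with CF-guided approach", takes a goal of 50%, and states that "a sample size of 150 is needed in order to have 95% power". With the exact two-sided 95% interval, the lower bound first exceeds 50% at 88/150. P(X ≥ 88 | n = 150, p = 0.65) = 95.5%, so the stated power reproduces. 150 / (1 − 0.20) = 187.5, rounded up to 188, which also reproduces ("Considering 20% dropout rate, a sample size of 188 is needed"). The same rule needs 108/188 or 115/200 successes.

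**2. Can a blanking re-ablation be a failure under the listed rules?**

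| Rule | Reaches a re-ablation within 90 days? |
|---|---|
| Repeat ablation after Day 90 | No, by definition |
| Acute failure, including use of a non-study catheter | Not clearly: it sits under acute procedural failure, and Protocol 4.2.1 ties it to the initial ablation |
| Later symptomatic AF/AT/AFL or later repeat ablation | Only if that later event happens |
| Not followed to the endpoint (SAP 6.5.1) | Only if follow-up is incomplete |

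A re-ablated subject with none of these later events is an ITT success.

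**3. Size of the difference.** Let q be the share of all subjects who are re-ablated in blanking and then counted as successes. Single-procedure rate = ITT rate − q. The documents give no value for q. Illustration with 200 subjects and 65% success (130), 10 of the successes re-ablated in blanking (q = 5%):

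- current ITT rule: 130/200 = 65.0%
- removed, as PP appears to do: 120/190 = 63.2%
- counted as failures: (130 − 10)/200 = 60.0%

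No planned analysis yields the last figure. From 130/200, reclassifying 16 subjects (8%) gives 114/200, with a lower bound of 49.8%, and the criterion is no longer met.

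**4. Probability of a false claim about the single-procedure rate.** Assumptions: true single-procedure rate 50%; a share r of subjects re-ablated in blanking; 65% of those then event-free (the planning rate for the whole cohort, borrowed here); a share d lost to follow-up, unrelated to outcome. SAP 6.5.1 counts lost subjects as failures in the main analysis, so

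ITT rate = (1 − d) × (0.50 + 0.65r), and the probability is P(X ≥ 108 | n = 188).

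| Loss d | r = 0 | r = 2% | r = 5% | r = 8% |
|---|---|---|---|---|
| 0% | 2.4% | 5.3% | 14.0% | 29.3% |
| 5% | 0.4% | 1.0% | 3.5% | 9.6% |
| 20% (planned) | <0.01% | <0.01% | <0.01% | 0.02% |

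Example: d = 5%, r = 5% gives 0.95 × (0.50 + 0.0325) = 0.506 and a probability of 3.5%. Both r and the 5% loss are assumptions; the 20% loss is the plan's own figure.

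**The case against.** - **The endpoint is deliberate.** The protocol chose the 90-day limit and cites published guidance for its handling of blanking. Against that definition the one-sided error stays at 2.4% for n = 188. The 50% goal rests on one of the same sources, and the documents do not show whether it counts blanking re-ablation as failure. This stands: the point concerns what the estimate means, not a breach of the plan's own test. It is why the primary definition can stay.
- **A reader might infer a large inflation of false claims.** The 14% and 29% figures need complete follow-up and re-ablation shares that the documents do not support. At 5% loss they fall to 3.5% and 9.6%, and at the planned 20% to at most 0.02%. The objection stands in full.
- **A reader might infer that these subjects can never fail.** They can, through a later symptomatic recurrence, a later repeat ablation, acute failure or incomplete follow-up. Only the early re-ablation itself goes uncounted.
- **A reader might take exclusion from PP as settled.** It rests on a broken sentence, possibly a layout or translation fault. If exclusion is intended, PP moves part of the way towards the stricter figure (63.2% in the illustration), and the listing of major deviations under SAP 6.3.2 would already show these subjects.
- **It may be rare.** That is possible, since the protocol advises against it. If none occur, the added analysis equals the main one.

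**Conclusion.** The concern holds in a limited form. The endpoint is anchored to the index ablation, re-ablation in blanking is permitted, and no planned analysis treats it as failure of the index procedure or gives the single-procedure rate. The overstatement equals the share re-ablated in blanking and then counted as successes. That share is unknown; 5 percentage points is an illustration, not an estimate. The documents do not support saying that the superiority test is invalid or that its error is materially inflated: that depends on the re-ablation share, on success after re-ablation and on loss to follow-up, and at the planned 20% loss the effect is negligible. The stated sample sizes of 150 and 188 are unaffected. This is a gap in interpretation and reporting that should be closed because it is cheap to close.

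**What to change.** 1. Leave the primary definition unchanged. In SAP 6.5.1 add an ITT sensitivity analysis in which any repeat ablation after the index procedure, including within 90 days, is a failure.
2. Add a matching Kaplan-Meier analysis. An event before Day 91 does not fit the Day 91 to 361 curve, so either start the curve at the index procedure or count these subjects as events at Day 91, and say which.
3. Extend the summary of re-ablations in SAP 6.5.1 to give the number performed during blanking.
4. Repair the sentence in SAP 6.2.3 so that handling in PP is explicit. If these subjects are excluded, report how many.

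Cost: one extra analysis and a small edit. Protocol 5.7 already requires every re-ablation to be documented in the CRF, so no new data are needed. The downside is a supportive figure that may be less favourable.
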